Study Enrollment and Consent: After the vaccine is administered (or the patient declines the vaccine), a member of the research team (RA) will approach eligible postpartum women and invite them to participate in individual in-depth interviews. The RA will obtain informed consent (see attached) from women willing to participate. If an in-person interview prior to hospital discharge is not possible, the RA will contact patients by phone within 2 weeks of hospital discharge and explain study purpose and interview and subjects will be given option to participate in a phone interview. In the case of a phone interview, informed consent will be sent to patient electronically via encrypted email, reviewed over phone and patient will electronically sign and return consent before proceeding with the interview. If patient is unable to sign consent electronically, they will be given option to sign it in person during their next postpartum encounter at the Women's Center and then have the option of being interviewed before or after their clinic encounter that day or via a follow up phone call. If unable to reach the patient by phone, we will approach the patient at her Women's Center postpartum appointment after obtaining permission from her visit provider and invite the patient to participate in an interview. The RA will obtain consent at that time from women willing to participate. After being consented, the patient will have the option of being interviewed before or after their clinic encounter that day or via a follow up phone call. A \$25 Visa card will be provided as an incentive to women who participate.

Sampling: We will select a purposive sample of postpartum women into two groups: those who receive inpatient HPV vaccine and those who decline the inpatient dose to interview until we reach thematic saturation which we anticipate to occur with about 8-10 individuals per group. Patients will be selected to include diverse representation in age, race, ethnicity, and parity.

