123 **Data collection:** We will conduct in-person, in-depth interviews prior to discharge home from the postpartum hospitalization. If an in-person interview prior to discharge is not possible, we will conduct phone interviews or interview at the outpatient postpartum visit as described above. We will conduct interviews using a semi-structured guide (see attached) with questions based on Consolidated Framework for Implementation Research (CFIR) constructs. We will maintain an open-ended format that allows the interviewer to probe with questions as needed to engage participants to use their own words to express experiences. We will focus on CFIR constructs belonging to domains we consider to be most relevant to IPP-HPV implementation from the patients' perspective: *Intervention Characteristics* (e.g., perceived advantages and adaptability of the intervention) and *Characteristics of Individuals* (e.g., knowledge and beliefs about the intervention).

124 **Data analysis:** All interviews will be recorded and subsequently transcribed. We will analyze transcripts and determine common themes and priority domains. Standard analytic methods for qualitative data will be employed. A codebook will be developed based on deductive (theory-driven) constructs from the interview guide and applied to a subset of transcripts. Concordance will be measured and discrepant

codes resolved by adjudication using software for qualitative research. We will identify and discuss initial themes and identify inductive (data-driven) codes. The identification of inductive codes will continue with subsequent coding in an iterative manner. Results will be shared and discussed with other investigators for final analysis and interpretation to determine what changes can be made (incorporating findings from Aim 2 as well) to improve the IPP-HPV intervention for future implementation.

1.3 Specific Aim 2

To evaluate receptivity and concerns of healthcare providers with inpatient postpartum HPV immunization as part of IPP-HPV and to identify facilitators of and barriers to its implementation.

1.3.1 Study participants: YNHH inpatient and Women's Center outpatient postpartum nurses and obstetric providers affiliated with the Women's Center or Center for Women's Health and Midwifery, including nursing and medical directors, will be eligible to participate.

1.3.2 Study design:

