We will obtain data on receipt of subsequent doses of vaccine and on completion of the 3-dose series of the vaccine by medical chart review. Dates of receipt of HPV vaccine, date of postpartum visit, and data on whether a dose of HPV vaccine was due at the postpartum visit and, if so, whether dose was received will be recorded. Data on the need for and receipt of postpartum Tdap, influenza and rubella vaccines will also be obtained from medical chart review for comparison. Demographic and clinical information will also be obtained. Historical data on the HPV vaccination history of all WC patients \leq 26 years old who delivered in the 12 months prior to implementation of IPP-HPV will also be collected for comparison of their rates of vaccine series completion (from outpatient administration) within 30 months of delivery.

144

Data analysis: We will tabulate measures as follows:

- IPP-HPV Acceptance: Proportion of eligible patients agreeing to receive a dose of vaccine
- HPV Vaccine Administration: Proportion of eligible patients that agree to be vaccinated who actually receive dose of vaccine as an inpatient.
- Barriers to vaccination: descriptive data on potential barriers to receiving the vaccine postpartum
- Other vaccines: Proportion of eligible patients due for Tdap, influenza or MMR vaccines and proportion that receive each

To assess the effectiveness of the pilot IPP-HPV immunization program we will tabulate the proportion of postpartum women eligible for the vaccine who receive a dose of HPV vaccine, the proportion of participants that need 1, 2, or 3 vaccine doses that receive the respective number of doses within up to 30 months of postpartum discharge, the proportion of all participants that complete the vaccine series within 12 months and within 30 months, and the proportion of study participants that complete the vaccine series within 12 months and within 30 months that received IPP-HPV.

Multivariable logistic regression will be used to determine predictors of inpatient postpartum HPV vaccine uptake and of vaccine completion (e.g., age, parity, race, ethnicity). The difference in proportion of women who complete the 3-dose series within 12 months and within 30 months of postpartum discharge in the study cohort and in the group of Women's Center patients who delivered in the 12 months prior to implementation of IPP-HPV will be compared using chi square analysis.

1.5 Specific Aim 4

151 Study participants:

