6. **Subject classification:** Check off all classifications of subjects that will be specifically recruited for enrollment in the research project. Will subjects who may require additional safeguards or other considerations be enrolled in the study? If so, identify the population of subjects requiring special safeguards and provide a justification for their involvement.

 Children	 Healthy	 Fetal material, placenta, or dead fetus
 Non-English Speaking	 Prisoners	 Economically disadvantaged persons
 Decisionally Impaired	 Employees	 Pregnant women and/or fetuses
 Yale Students	 Females of childbearing potential	

NOTE: Is this research proposal designed to enroll children who are wards of the state as potential subjects? **Yes** **No**

7. **Inclusion/Exclusion Criteria:** What are the criteria used to determine subject inclusion or exclusion?

Specific Aim 1: Patient Qualitative Interviews

Inclusion:

- Women participating in the IPP-HPV Quality Improvement Program:
 - Postpartum YNHH Women's Center and CWHM patients
 - ≤ 26 years at time of delivery who deliver at YNHH YSC or SRC
 - Have not already received 3 doses of the HPV vaccine at time of delivery
- Fluent in English or Spanish
- Able and willing to provide consent

Specific Aim 2: Provider Qualitative Interviews

Inclusion:

- YNHH inpatient postpartum nurses or Women's Center outpatient postpartum nurses or inpatient or outpatient obstetric providers affiliated with the Women's Center or Center for Women's Health and Midwifery
- Able and willing to provide consent

Specific Aim 3: Medical Records Review

Inclusion:

- Yale New Haven Hospital (YNHH) Women's Center and Center for Women's Health

and Midwifery (CWHM) postpartum patients

- ≤ 26 years of age
- Delivered at YNHH York Street Campus (YSC) or Saint Raphael Campus (SRC) in the first year of the IPP-HPV program or in the one year preceding implementation of the program

Specific Aim 4:

Observational Workflow Analysis

Inclusion:

- YNHH (YSC or SRC) inpatient postpartum nurses or inpatient obstetric providers

Provider/Staff Qualitative

Interviews Inclusion:

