A number of precautions will be actively integrated into study procedures to protect confidentiality. (1) For the qualitative data analysis, all data will be presented anonymously. Themes and quotes will be designated by the race/ethnicity, preferred language, age of patient, outpatient obstetrics site, and HPV vaccination completion status only, as these are the key variables of interest. Participants will be assured that the information they provide will not be linked to them as individuals in any study reports, publication or presentations. (2) All quantitative data will be analyzed collectively so that information from any individual will remain anonymous. (3) Study participants will be protected by having all information obtained by the research staff designated by a unique study identification number only, assigned to the participant at the time of his or her entry into the study. Only this code and no identifying information (e.g. names) will be maintained in data files. A separate master list of names and medical record numbers along with study identification numbers will be maintained in a password protected computer file. Access to the computers and data files stored on other media (e.g. flash drives) will be limited both physically (e.g. in locked offices) and electronically (e.g. on encrypted computers). All data files will be password protected and stored on a secure server. All paper records including consent forms will be kept in locked file cabinets. (4) The information obtained will be used for the purposes of data analysis only. (5) Upon completion of the data collection phase, the data will be "de-identified" meaning that the identifying information (namely medical record number) will be separated from the clinical variables collected. The prompt removal of identifying information will help to limit the risk of breaches of confidentiality. Once all data analysis has been completed, the master list containing the patient's medical record number will be destroyed in a manner approved by Yale for materials containing sensitive patient health information.

11. Data and Safety Monitoring Plan: Include an appropriate Data and Safety Monitoring Plan (DSMP) based on the investigator's risk assessment stated below. (Note: the HIC will make the final determination of the risk to subjects.)

- a. What is the investigator's assessment of the overall risk level for subjects participating in this study? Minimal

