All individual interviews will be recorded and subsequently transcribed. We will analyze transcripts and determine common themes and priority domains. Standard analytic methods for qualitative data will be employed.¹⁵ A codebook will be developed based on deductive (theory-driven) constructs from the interview guide and applied to a subset of transcripts. Concordance will be measured and discrepant codes resolved by adjudication using software for qualitative research. We will identify and discuss initial themes and identify inductive (data-driven) codes. The identification of inductive codes will continue with subsequent coding in an iterative manner. The coded data will be used to develop process maps for each vaccine and understand the needs and preferences of each provider group, as it relates to an EMR-based tool for IPP-HPV immunization.^{51,52} All individual surveys will be recorded and kept anonymous. Participants will be provided a QR code to complete the survey using the Yale Qualtrics platform. We will analyze the knowledge, attitudes, and beliefs of participants in aggregate and by delivery network using descriptive statistics, bivariate and multivariate analyses.

SECTION II: RESEARCH INVOLVING DRUGS, BIOLOGICS, RADIOTRACERS, PLACEBOS AND DEVICES

If this section (or one of its parts, A or B) is not applicable, state N/A and delete the rest of the section.

N/A

SECTION III: RECRUITMENT/CONSENT AND ASSENT PROCEDURES

1. Targeted Enrollment: Give the number of subjects:

a. Targeted for enrollment at Yale for this protocol:

Specific Aim 1: 16-20 patient interviews

Specific Aim 2: 15 provider interviews

Specific Aim 3: 700 medical charts reviewed

Specific Aim 4: 15-20 unique observations and 15-20 interviews with OB providers and nurses and 8-10 interviews with hospital pharmacy and YNHH EMR representatives

Specific aim 5: 15-20 interviews with OB providers and nurses and 8-10 interviews with hospital pharmacy and YNHH EMR representatives. 50 completed surveys from OB related healthcare workers from each of #4 YNHHS sites.

b. If this is a multi-site study, give the total number of subjects targeted across all sites:

N/A

2. Indicate recruitment methods below. Attach copies of any recruitment materials that will be used.

- Flyers
- Posters
- Letter
- Medical Record Review*
- Departmental/Center Newsletters

- Internet/Web Postings
- Mass E-mail Solicitation
- Departmental/Center Website
- Departmental/Center Research Boards

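### Aim 1 samples women by whether they received or declined the inpatient dose, but the closed list of labels allowed on themes and quotes omits that variable, and completion status does not replace it

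*Combined protocol and SAP*

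**What the plan says.** **Sampling.** Section I.3, item 122 (Aim 1, Sampling), repeated in Section I.5, forms two purposive groups: "those who receive inpatient HPV vaccine and those who decline the inpatient dose to interview until we reach thematic saturation". Saturation is expected at a stated size: "which we anticipate to occur with about 8-10 individuals per group". Section III.1 gives the total: "Specific Aim 1: 16-20 patient interviews".

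**Eligibility.** Section I.7 requires of each woman: "Have not already received 3 doses of the HPV vaccine at time of delivery".

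**Timing of interviews.** Item 123 gives the default: "We will conduct in-person, in-depth interviews prior to discharge home from the postpartum hospitalization". Items 122 and 123 give the fallbacks: a phone interview after contact within two weeks of discharge, or an interview around the outpatient postpartum visit, which may be after the encounter or by a later call.

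**Reporting rule.** Section I.10 (Minimizing Risks), first confidentiality precaution: "Themes and quotes will be designated by the race/ethnicity, preferred language, age of patient, outpatient obstetrics site, and HPV vaccination completion status only". The same sentence ends by giving its reason: "outpatient obstetrics site, and HPV vaccination completion status only, as these are the key variables of interest". The reference to the patient's age shows that the rule covers the patient interviews.

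**Use of 'completion' elsewhere.** In the Aim 3 analysis (Section I.3, item 144) the word refers to the vaccine series over follow-up: "the proportion of all participants that complete the vaccine series within 12 months and within 30 months". Section I.12 uses it the same way at 12 months.

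**Analysis of Aim 1.** Item 124 and Section I.12 describe coding, common themes and use of the findings to improve the program. Neither mentions the two sampling groups.

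**The concern.** The one vaccine variable that shapes the Aim 1 sample is whether the woman took the dose offered in hospital. The rule on presentation closes its list with the word only and leaves that variable out. It lists completion status instead, which answers a different question.

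Aim 1 concerns how women receive the offer of an inpatient dose and what worries them about it, and the results are meant to guide changes to the program. To use a reported concern, a reader needs to know whether it came from a woman who accepted the dose or from one who declined. A concern voiced by women who nevertheless accepted calls for a different response from one that led women to refuse. Followed to the letter, Section I.10 keeps that information off every theme and quote. Nothing in the Aim 1 analysis text restores it.

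**Working it through.** **1. The plan's own figure.** Two groups of 8 to 10 give 2 × 8 = 16 and 2 × 10 = 20. This matches the 16-20 interviews in Section III.1, so the target is built on the received/declined split.

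**2. The label list against the sampling variable.** Section I.10 permits five labels: race or ethnicity, language, age, outpatient site and completion status. The sampling variable is received or declined. It is not on the list, and only completion status has to do with vaccination.

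**3. Can completion status stand in for the group before discharge?** The series has three doses, and every eligible woman enters with 0, 1 or 2.

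| Prior doses | Received inpatient dose | Declined |
|---|---|---|
| 0 | incomplete | incomplete |
| 1 | incomplete | incomplete |
| 2 | complete | incomplete |

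Only one of the six cells is complete.

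**4. Size of the overlap.** Let n be the number per group and q the share of recipients with two prior doses. The documents do not give q, so it is varied as an assumption.

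- Complete: n × q
- Incomplete: n × (1 − q) + n = n × (2 − q)
- Share of the incomplete who received the dose: (1 − q) / (2 − q)

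| Assumed q | Incomplete, n = 8 (of 16) | Incomplete, n = 10 (of 20) | Share of incomplete who received the dose |
|---|---|---|---|
| 0 | 16.0 | 20 | 50% |
| 0.1 | 15.2 | 19 | 47% |
| 0.2 | 14.4 | 18 | 44% |
| 0.3 | 13.6 | 17 | 41% |
| 0.5 | 12.0 | 15 | 33% |

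For example, n = 10 and q = 0.2 gives 10 × 1.8 = 18 incomplete, of whom 8 received the dose: 8 / 18 = 44%. The share reaches zero only at q = 1, that is, if every sampled recipient had two prior doses. Nothing in the documents suggests this.

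**5. Does a later status do better?** Labels are attached when results are reported, so a later status could be used. But a decliner may then have completed the series as an outpatient, and a recipient with doses still due may not have. Complete and incomplete then each can hold women from both groups.

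**The case against.** The strongest case on the other side has five parts.

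- **The rule is a confidentiality safeguard, not an analysis rule.** This stands. Nothing in Section I.10 stops the team from coding, comparing or interpreting by sampling group. A reader might infer that the plan forbids or forgoes the comparison; the documents do not say so. The restriction falls on what may be shown beside a theme or quote.
- **Completion status is not the only label.** This also stands. The word only closes a list of five attributes. A reader might infer that quotes carry completion status and nothing else, which is wrong; it is the only vaccine-related label.
- **Timing.** A reader might infer that the label fails because completion is unknown at interview. The documents do not support that. Status on the interview date is knowable, labels are applied at reporting, and Section III.6 obtains permission to access clinic records to confirm vaccine histories. Also, the statement that all decliners are incomplete is secure only before discharge: at an interview after the postpartum visit, a decliner with two prior doses could have received her third there. The fault is in the choice of variable.
- **Meaning of the term.** Section I.10 does not say series. The phrase may have been meant loosely for the inpatient dose. That is possible, though the Aim 3 text points the other way, and the ambiguity is itself a reason to define the term.
- **No formal contrast is stated.** Sampling both groups to saturation may aim at coverage of both views. This is fair, but a report that covers both views still needs to say which view is which.

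None of these puts the missing label on the list.

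**Conclusion.** The point holds as a gap between the sampling plan and the reporting rule. The attribute that defines the two Aim 1 groups is absent from a closed list of permitted labels, and the one vaccine-related label on that list does not recover it. Read literally, the rule keeps the report from attributing themes or quotes to recipients or decliners.

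Before discharge, with 10 women per group and an assumed 0 to 50% of recipients having two prior doses, the incomplete label covers 20 down to 15 of 20 women and mixes both groups throughout. This rests on reading completion as series completion and on the assumed range of q. The omission from the list rests on neither.

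The effect is confined to how Aim 1 is reported. No sample size, error rate or quantitative result is affected. The change is worth making because it bears directly on what Aim 1 can tell a reader and costs little.

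**What to change.** In Section I.10, add inpatient HPV dose received or declined to the labels permitted for Aim 1 themes and quotes, or substitute it for completion status. If completion status is kept, state whether it means the three-dose series and at what date it is taken, and confirm that the records permission in Section III.6, which is worded around confirming vaccine histories, covers later follow-up.

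The cost is a phrase in the protocol. The group is known for every interviewee, so no new data are needed. There is one small downside: if the label is added rather than substituted, each quote carries one more attribute in a sample of only 16-20 women, so another label may have to be coarsened (age in bands, for instance) or dropped to keep the confidentiality commitment. Substitution keeps the list at five labels.

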1.42 **Study design:** Medical record review from above patients to review each patient’s immunization record and related clinical visits in the 30 months after delivery.

1.43 **Data Collection:**
The following data will be recorded from the chart (i.e., MRN, name, diagnosis):

- MRN
- Patient ID
- Name
- DOB
- Race
- Ethnicity
- Marital status
- Religion
- Primary Language
- Education
- Zip Code
- Insurance Type (Payor Name, Benefit Class, Benefit Plan Name)
- Smoking Status
- Gravidity
- Parity
- HIV status
- Allergies
- Number of clinic visits to WC or CWHM during 30 months following delivery
- Provider Name
- Provider Type
- Dates of visits
- Visit type
- HPV vaccination status at each encounter
- Dates that each HPV vaccine was ordered.
- Vaccine Type (i.e., quadrivalent vs 9-valent, etc)
- Vaccine number/rank (#1, 2, or 3 in the series)
- Name of provider who ordered each vaccine.
- Date that each HPV vaccine was administered.
- Were any other vaccines administered during the 30 months following delivery?
- If yes, which ones and on what dates?
- Were any other injectable medications administered during the study period?
- If yes, which ones and on what dates?

- Was HPV vaccine due?
- Was HPV vaccine offered/discussed?
- Was HPV vaccine ordered?
- Was HPV vaccine administered?
- Was HPV vaccine declined?
- If declined, what was the reason for decline?
- Were other postpartum vaccines (Tdap, flu, MMR) due?
Administered/declined?

Measures that will be used from the IPP-HPV program to assess its implementation will include number of women eligible for HPV vaccine, proportion accepting a dose of HPV vaccine while inpatient, proportion who agree to be vaccinated but do not receive the vaccine dose, and identification of possible barriers to implementation of IPP-HPV (e.g., nurses are too busy, patients leave prior to vaccine administration, vaccine order not placed). In addition, we will abstract data from questionnaires voluntarily submitted by postpartum nurses to the IPP-HPV Program on their experience with each patient related to HPV immunization.

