To evaluate receptivity and concerns of healthcare providers with inpatient postpartum HPV immunization as part of IPP-HPV and to identify facilitators of and barriers to its implementation.

Study participants: YNHH inpatient and Women's Center outpatient postpartum nurses, and obstetric providers affiliated with the Women's Center or Center for Women's Health and Midwifery, including nursing and medical directors, will be eligible to participate. We will aim to have a purposive sample of about 15 participants with representation by provider type and clinical setting/location.

Specific Aim 3

To assess the uptake and effectiveness of a Pilot Quality Improvement Program to increase HPV vaccine uptake (IPP-HPV) for Yale New Haven Hospital (YNHH) Women's Center and Center for Women's Health and Midwifery (CWHM) postpartum patients \leq 26 years of age who deliver at YNHH

York Street Campus (YSC) or Saint Raphael Campus (SRC).

Study participants: Women's Center and CWHM postpartum patients \leq 26 years of age who have received less than 3 doses of the HPV vaccine prior to delivery and who deliver at YNHH YSC or SRC during the first year of the IPP-HPV Program as well as Women's Center and CWHM postpartum patients \leq 26 years of age who delivered at YNHH YSC/SRC in the year preceding implementation of the IPP-HPV Program.

Specific Aim 4

To identify the processes utilized to integrate delivery of vaccines that are currently administered routinely during inpatient postpartum care

Study participants: Observational workflow analysis-YNHH (YSC or SRC) inpatient postpartum nurses or inpatient obstetric providers; In-depth individual interviews--YNHH

(YSC or SRC) inpatient postpartum nurses, inpatient obstetric providers, hospital pharmacy representatives or EMR analysts

Specific Aim 5

To iteratively develop an EMR-based tool that promotes integration of IPP-HPV immunization into routine inpatient postpartum care and conduct a survey prior to implementation of IPP-HPV to assesses the knowledge, attitudes and beliefs of HPV vaccine and IPP-HPV by OB healthcare workers across YNHHS.

Study participants: YNHHS inpatient postpartum nurses, inpatient obstetric providers, hospital pharmacy representatives or EMR analysts

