To assess the effectiveness of the pilot IPP-HPV immunization program we will tabulate the proportion of postpartum women eligible for the vaccine who receive a dose of HPV vaccine, the proportion of participants that need 1, 2, or 3 vaccine doses that receive the respective number of doses within 12 months of postpartum discharge, the proportion of all participants that complete the vaccine series within 12 months, and the proportion of study participants that complete the vaccine series within 12 months that received IPP-HPV.

Multivariable logistic regression will be used to determine predictors of inpatient postpartum HPV vaccine uptake and of vaccine completion (e.g., age, parity, race, ethnicity). The difference in proportion of women who complete the 3-dose series within 12 months of postpartum discharge in the study cohort and in the group of Women's Center patients who delivered in the 12 months prior to implementation of IPP-HPV will be compared using chi square analysis.

Specific Aim 4:

All workflow analysis and individual interviews and will be recorded and subsequently transcribed. We will analyze transcripts and determine common themes and priority domains. Standard analytic methods for qualitative data will be employed.¹⁵ A codebook will be developed based on deductive (theory-driven) constructs from the interview guide and applied to a subset of transcripts. Concordance will be measured and discrepant codes resolved by adjudication using software for qualitative research. We will identify and discuss initial themes and identify inductive

(data-driven) codes. The identification of inductive codes will continue with subsequent coding in an iterative manner. The coded data will be used to iteratively develop process maps for each vaccine and to identify gaps in the process to guide subsequent observations.⁵⁵ The maps will also indicate process variations and identify steps in which EMR tools are utilized.

Specific Aim 5:

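### The only named before-after test of Aim 3 completion is an unadjusted chi-square on two cohorts that the text does not define alike; define them alike and adjust for doses needed and clinic

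*Combined protocol and SAP*

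**What the plan says.** **The test.** Section 1.44 (Data analysis, Aim 3) and Section I.12 (Statistical Considerations, Aim 3) both contrast completion in the study cohort with completion in Women's Center "patients who delivered in the 12 months prior to implementation of IPP-HPV will be compared using chi square analysis". Section 1.44 gives 12 and 30 months; Section I.12 gives 12 months only. No adjustment is mentioned.

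**The model.** "Multivariable logistic regression will be used to determine predictors of inpatient postpartum HPV vaccine uptake and of vaccine completion". Its covariates are examples only: "of vaccine completion (e.g., age, parity, race, ethnicity". Neither period nor doses needed is named, and the text does not say whether prior-year women enter the model.

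**Doses needed.** These appear only in a tabulation: "the proportion of participants that need 1, 2, or 3 vaccine doses that receive the respective number of doses within 12 months" (Section I.12; Section 1.44 extends the window to 30 months).

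**The cohorts.**
- Sections 1.41 and I.5 limit program women to those with fewer than 3 prior doses. The prior-year clause covers Women's Center and CWHM women "who delivered at YNHH YSC/SRC in the year preceding implementation of the IPP-HPV Program" and states no dose limit.
- Section I.7 gives no dose rule for either period.
- Section 1.43 collects "Historical data on the HPV vaccination history of all WC patients" aged 26 or under, which names one clinic and again no dose limit.
- Section 1.41 takes two program years; Sections I.5 and I.7 take the first year.

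**The data.** Section 1.43 abstracts "HPV vaccination status at each encounter", "Vaccine number/rank (#1, 2, or 3 in the series", vaccination dates, age, parity, race, ethnicity and insurance. Section III.1 targets 700 charts in total and gives no split by period.

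**The concern.** Two features of the text could make the groups unlike before the program has any effect.

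The first is prior doses. If prior-year women who had already finished the series are kept, they cannot complete it after delivery. They either count as completers or sit in the denominator as women who cannot complete within the window, and these two treatments push the contrast in opposite directions. Even among women with fewer than 3 doses, one who needs a single dose has fewer steps left than one who needs three. A change in that mix between periods would be read as a program effect, or would hide one.

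The second is clinic. If the comparator is Women's Center only while program women come from both clinics, any difference in completion between the clinics enters the contrast.

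At stake is the one between-period test of completion. Aim 3 is partly about effectiveness, and Section V says that documenting effectiveness would help expand the program.

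**Working it through.** There is no planned figure to reproduce: the 700 charts come with no alpha, power, expected rates or effect size. Two-sided 0.05, the splits of 700 and every mix and rate below are assumptions.

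**1. Unequal dose rule.** Let a share c of prior-year women have completed before delivery, let 23.8% of all other women in both periods complete afterwards, and let the program do nothing.
- Counted as completers: difference = 0.238 − [c + (1 − c) × 0.238]. This is −7.6 points at c = 10% and −22.9 at c = 30%.
- Kept in the denominator as non-completers: difference = 0.238 − (1 − c) × 0.238. This is +2.4 points at c = 10% and +7.1 at c = 30%.

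The sign depends on a rule that the text does not state.

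**2. Unequal clinics.** If a share w of program women are CWHM and none of the comparators are, the crude difference moves by w × (CWHM completion − Women's Center completion). The documents give neither quantity.

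**3. Doses needed, among women with fewer than 3 doses.** Crude completion = sum of (mix × rate). The prior-year mix needing 1/2/3 doses is 10/15/75%. The share already started rises by 2.3 points (split 40:60 between needing 1 and 2), 8 points (15/18/67) or 15 points (20/20/60). Rates are the same in both periods, so there is no program effect. Steep gradient, 8-point rise: 0.15 × 45 + 0.18 × 25 + 0.67 × 10 = 17.95%, against 0.10 × 45 + 0.15 × 25 + 0.75 × 10 = 15.75%, a difference of 2.20 points.

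Rejection is from the pooled-variance two-proportion formula, both tails, at 350/350:

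| Completion needing 1/2/3 | Difference, points (+2.3 / +8 / +15) | Crude rejection |
|---|---|---|
| 45/25/10% | 0.53 / 2.20 / 4.25 | 5.4 / 12.1 / 31.1% |
| 30/22/14% | 0.26 / 1.04 / 2.00 | 5.1 / 6.5 / 10.6% |
| 25/20/15% | 0.16 / 0.65 / 1.25 | 5.0 / 5.6 / 7.2% |

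At 233/467 the 8- and 15-point rises give 10.8% and 26.9% (steep), 6.2% and 9.5% (shallow), and 5.4% and 6.7% (shallowest).

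The base mix is not far from the Background section. National initiation of 30% and completion of 13% imply that (30 − 13)/(100 − 13) = 17/87, about 20%, of non-completers had started. Rebasing to 8/12/80 changes little: 12.6% and 32.5% (steep), 6.6% and 10.8% (shallow).

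**4. Masking.** Take a true +8 points in every stratum and an 8-point fall in the share already started (5/12/83), at 350/350:
- steep: +8 becomes +5.8, and power falls from 76% to 50%;
- shallow: +7.0, from 74% to 63%;
- shallowest: +7.35, from 74% to 67.5%.

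**5. Is adjustment workable?** In one set of simulations (4,000 runs per cell), a logistic model with 11 parameters (period, doses needed, age, parity, race/ethnicity, insurance) rejected 4.4–5.7% of the time with no effect. In the masking case its power was 81% (steep) and 74% (shallow). The steep figure exceeds the 76% crude power with no shift, so about 5 points of it are not bias removed and are plausibly precision gained. Doses needed was the only confounder simulated, so error control holds by construction. The runs show only that a model of this size can be fitted.

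Those runs had no clinic term. One binary clinic term makes 12 parameters, or 6 in a reduced model of period, doses needed, clinic and age. At an assumed 13–16% completion, 700 charts give 91–112 completions: 91/12 = 7.6 to 112/12 = 9.3 per parameter in the full model, and 91/6 = 15.2 to 112/6 = 18.7 in the reduced one.

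**The case against.** **The bias is hypothetical.** These are delivery years close together, with the same age limit and delivery campuses, and nothing in the documents says that the dose mix changed. This stands as a limit on size. Most of the rejection rates in the table lie close to 5%, and the largest needs a 4.5-fold gradient (45% against 10%).

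**The plan leaves room.** The covariate list is open, and Sections 1.41 and I.5 list both cohorts as study participants. Period and doses needed could enter the model, and the table by doses needed might cover both cohorts. This stands in part. The plan does not say so, the chi-square sentence separates the study cohort from the comparator, and a descriptive table does not adjust a test. Settling the model after seeing the data leaves the choice open to the result.

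**It is a pilot about implementation.** The Background section states that purpose, so a crude test is not an internal error. That is accepted.

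**Stronger readings.** A reader might infer that the cohorts do differ in dose history, or that prior-year completers will be counted. The documents show neither. The missing dose limit and the single-clinic wording may be loose drafting, and no dose distribution or completion rate by doses needed is given for either period.

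**Conclusion.** The point holds in limited form. The text shows an unadjusted chi-square as the only named between-period test of completion, a dose limit attached to one cohort only, and two descriptions of the comparator's clinics. The direction of any bias is open and its size is unknown. Under the assumed mixes and rates, a shift in doses needed is material only if both the shift and the completion gradient are large. The unequal dose rule could matter more, by several points in either direction at the assumed shares, if it is applied as written. It would be wrong to conclude that the planned test will give a false positive, or that the program's effect will be misjudged. This is a cheap improvement to the stated method.

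**What to change.** 1. Apply the same rule of fewer than 3 prior doses and the same clinics to both cohorts. Reconcile Sections 1.41, 1.43, 1.44, I.5, I.7 and I.12 on clinics, on one or two program years, and on 12 or 12 and 30 months.
2. Make the main comparison a logistic regression on the pooled cohorts with a period term, adjusted for doses needed at delivery (1/2/3), clinic, age, parity, race/ethnicity and insurance. If completions are few, reduce it to period, doses needed, clinic and age. If the comparator stays Women's Center only, restrict the main comparison to Women's Center women in both periods, because clinic cannot then be separated from period for CWHM women.
3. Report the standardised difference in completion with a 95% CI at each planned time point, show completion by doses needed in each cohort, and keep the chi-square as the unadjusted result.
4. State that adjustment does not remove secular trend, so the adjusted difference is still not a causal estimate.

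The cost is plan wording, some derivation of doses needed from fields already abstracted, and a slightly less simple main analysis. Restricting to Women's Center would also leave fewer charts for the main comparison, by a number the documents do not give.
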